## **9.3 Missing Data**

Missing data in OKS will be imputed when calculating the OKS score using the method recommended by the new OKS scoring system. Missing data in 2011 KSS will be imputed when calculating KSS scores with the method recommended in the user manual of the 2011 Knee Society knee scoring system. No other missing data will be imputed.

## **9.4 Statistical Methodology**

### **9.4.1 Data Summary**

Descriptive statistics will be computed for all baseline conditions and demographic parameters. That is, for continuous data, the N, mean, median, standard deviation, minimum and maximum will be computed. For categorical data, the frequency will be computed. The data will be presented by appropriate subgroups (e.g., center).

A Kaplan-Meier survivorship curve will be displayed for revision and/or removal of the Triathlon Tritanium Tibial Baseplate for aseptic loosening for cementless cohort.

For the additional data collected according to Section 2.1.3, data will be summarized according to visits and cohorts. For parameters represented by continuous variables (e.g., ROM), the summaries will consist of the N, mean, median, standard deviation, minimum, and maximum values. For categorical variables (e.g., Gender from

CONFIDENTIAL

This material is the property of Stryker Orthopaedics. Do not disclose or use except as authorized in writing by Stryker.

Demographics), the frequency and percentage in each category will be presented. A paired t-test will be performed to evaluate the change in clinical and patient outcomes, preoperative to 10 years for cases with the Triathlon Tritanium Tibial Baseplate in cementless cohort. The 2011 KSS, OKS, and SF-12 will be compared and be presented with respect to improvement from preoperative to postoperative scores for both cohorts when applicable.

For the Follow-up Questionnaire, frequency and percentage will be computed for each category according to visits and cohorts. Applicable lists based on the Follow-up Questionnaire will be generated to capture AEs.

For radiographic data, data will be presented according to visits and cohorts for available parameters. Frequency and percentage will be computed for radiolucency according to visits. Radiographs will be evaluated according to the guidelines of The Knee Society total knee arthroplasty roentgenographic evaluation and scoring system.

Documentation of statistical analyses will utilize SAS software version 9.1.3 or higher.

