## **7.5 Annual Follow-up Visits**

### **7.5.1 Cohort 1 (cementless) Annual Follow-up Visits**

Cohort 1 (cementless) will be followed to 10 years postoperatively according to the following schedule. Clinical data will be collected via office visit by the investigator at the following annual postoperative intervals: 1-year, 2-year 5-year and 10-year. Tools for postoperative evaluation at each of these intervals will be the 2011 KSS, OKS, SF-12, AP, ML and Merchant radiographs. In the event that an in-person visit cannot be conducted and radiographs cannot be obtained, a Follow-up Questionnaire will be completed via mail, online completion (if available), or subject telephone interview with the subject by investigative site personnel.

The Follow-up Questionnaire, OKS and SF-12 will also be collected at the 3-year, 4-year, 6-year, 7-year, 8-year and 9-year intervals via mail, online completion (if available), or subject telephone interview with the subject by investigative site personnel. The questionnaire is used to obtain information on satisfaction, pain, complications and any study device revisions to enable calculation of the Kaplan-Meier Survival Curves.

All clinical data, radiographs, and patient outcomes data must be collected within  $\pm$  2 months of the 1-year and 2-year anniversary dates. For remaining annual time points, the window expands to  $\pm$  3 months of the 3-year anniversary date and  $\pm$  4 months of the 4-year through

CONFIDENTIAL

This material is the property of Stryker Orthopaedics. Do not disclose or use except as authorized in writing by Stryker.

10-year anniversary dates.

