#### **9.4.4 Analysis Population**

**Per Protocol Population:** The study population for analysis will include all non-censored subjects who receive the study devices and are available for efficacy evaluation. For details regarding study devices, see Section 6.1 and 6.2.

The primary and secondary efficacy analyses will be based on the per protocol population.

**Safety Population:** The safety population will include all non-censored subjects who received the study devices. For details regarding study devices, see section 6.1 and 6.2. For details regarding protocol-defined AEs, see Section 8.1.

The safety analysis will be based on the safety population.

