**Termination Reason**

**Date of Termination**

Death	Date of death
Investigative center termination	Date of study close-out visit
Lost to follow-up	Date Stryker termination approval given
Voluntary withdrawal	Date subject notified center of withdrawal
Revision/removal of study device	Date of revision/removal procedure
Study device not implanted	Date of surgery
Surgery not performed	Date Stryker termination approval given

At the time of study surgery it is required that the following components are implanted for each treatment group:

- Cohort 1 (cementless)
  - Triathlon Tritanium Tibial Baseplate
  - Triathlon Tritanium Patella
  - Triathlon CR or PS Beaded Femur with PA
  - Triathlon Tibial Insert
  
- Cohort 2 (cemented)
  - Triathlon Cemented Tibial Baseplate
  - Triathlon Cemented Patella
  - Triathlon CR or PS Cemented Femur
  - Triathlon Tibial Insert

Revision or removal of the Triathlon Tritanium Tibial Baseplate for aseptic loosening constitutes a failure for purposes of the primary endpoint. Revision or removal of the Triathlon Tritanium Tibial Baseplate for any reason requires study termination for the subject.

If revision of the Triathlon Tritanium Patella, Triathlon Beaded Femur or Triathlon Tibial Insert component is required during the study, the event does not constitute a failure or study termination for Cohort 1 (cementless). If revision of the Triathlon Cemented Patella, Triathlon Cemented Femur or Triathlon Tibial Insert component is required during the study, the event does not constitute a failure or study termination for Cohort 2 (cemented).

CONFIDENTIAL

This material is the property of Stryker Orthopaedics. Do not disclose or use except as authorized in writing by Stryker.

If the subject fails to return for his/her follow-up appointments, every effort should be made to contact the subject to assess his/her health status. If, after attempting to contact the subject through three documented phone calls and a certified letter, and the subject still does not respond, he/she will be considered lost to follow-up. A Study Termination eCRF will be completed **only after notifying Stryker of the subject's status** and **being given approval to terminate**.

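### The 10-year change in Cohort 1 scores is tested on completers only; a repeated-measures model would use the scores already collected from cases without a 10-year value

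*Combined protocol and SAP*

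**What the plan says.** Section 9.4.1 names one test for long-term change: "A paired t-test will be performed to evaluate the change in clinical and patient outcomes, preoperative to 10 years", to be run "for cases with the Triathlon Tritanium Tibial Baseplate in cementless cohort". The same section summarises the additional data by visit and cohort and presents improvement from preoperative to postoperative scores for both cohorts.

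Section 9.3 applies the published scoring rules to gaps within the OKS and 2011 KSS, then adds: "No other missing data will be imputed". Section 10.3 says: "Revision or removal of the Triathlon Tritanium Tibial Baseplate for any reason requires study termination for the subject". Under the same section, revision of the patella, femur or insert does not end participation. Section 9.4.4 defines the per-protocol population, which will "include all non-censored subjects who receive the study devices and are available for efficacy evaluation".

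On collection, section 7.5.1 says of the office visits: "Clinical data will be collected via office visit by the investigator at the following annual postoperative intervals: 1-year, 2-year 5-year and 10-year". It then says: "The Follow-up Questionnaire, OKS and SF-12 will also be collected at the 3-year, 4-year, 6-year, 7-year, 8-year and 9-year intervals". With the Cohort 1 evaluation schedule, this puts OKS and SF-12 preoperatively, at 6 weeks and every year from 1 to 10. KSS is collected preoperatively, at 6 weeks, at 6 months and at years 1, 2, 5 and 10.

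The plan specifies no longitudinal model and no sensitivity analysis for dropout, death or revision. Its only attrition figure is the 15% in section 9.4.2, which is attached to the 2-year primary endpoint.

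**The concern.** Ten years is a long time for a paired test to wait for its second score. A case that dies, is lost, or has its baseplate revised before then contributes nothing to the test, however many earlier scores it supplied. Baseplate revisions leave by rule, not by chance. The tested change therefore describes cases still under observation with the baseplate in place. It estimates the change for the whole cohort only if those who left would have changed by the same amount on average.

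Section 16 plans a 10-year publication, and the study advertisement in Appendix D presents long-term performance as a purpose of the study. A reader could easily take the tested change as the result for all treated cases. The test also forgoes whatever precision the earlier scores would add.

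**Working it through.** **The plan's own figure.** The documents give no number for the 10-year test, so the check starts with the calculation that carries the 15%. Inputs from section 9.4.2: reference 99%, margin 2%, one-sided 5%, power 95%.

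n = 0.99 × 0.01 × (1.645 + 1.645)² / 0.02² = 267.85, stated as 267. Then 267 / 0.85 = 314.1, rounded up to 315, as stated. The 15% is thus a 2-year planning allowance. Nothing carries it forward to 10 years.

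**Cases without a 10-year score.** Input: 356 cases in Cohort 1. The period over which the 15% is lost is an assumption. With a constant rate, the share kept is 0.85^(10/t), where t is that period in years.

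| Reading of the 15% | Share kept | Share left out | Cases left out of 356 |
|---|---|---|---|
| Total over 10 years | 0.850 | 15.0% | 53 |
| Lost by 5 years, then same rate | 0.85² = 0.722 | 27.8% | 99 |
| Lost by 3 years, then same rate | 0.85^(10/3) = 0.582 | 41.8% | 149 |
| Lost every 2 years | 0.85⁵ = 0.444 | 55.6% | 198 |

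More than half are left out only if the annual loss exceeds 1 − 0.5^(1/10) = 6.7%, which is 12.9% per 2 years.

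**Effect on the mean change.** Shift = share left out × (mean change in completers − mean change in the others). The gap is an assumption, because the documents give none.

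| Assumed gap (OKS points) | 15% left out | 55.6% left out |
|---|---|---|
| +3 | 0.15 × 3 = 0.45 | 0.556 × 3 = 1.67 |
| +5 | 0.15 × 5 = 0.75 | 0.556 × 5 = 2.78 |
| 0 | 0 | 0 |
| −3 | −0.45 | −1.67 |

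These shifts treat every missing case as having a 10-year score that was not observed. Patients who have died have no such score, which is one reason the plan must say what is being estimated.

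**How much leaves by rule.** At the plan's 99% reference rate, revision for aseptic loosening by 2 years would remove about 356 × 0.01 = 3.6 cases. The documents give no all-cause or 10-year figure.

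**The case against.** The strongest reply is that little depends on this test. It belongs to the additional data, has no hypothesis or decision rule, and is neither the primary endpoint nor the 2-year comparison between cohorts. Device failures are reported separately by Kaplan-Meier curves. The plan also works to limit loss: remote collection in the non-clinic years, three calls and a certified letter before a case counts as lost, reimbursement in some circumstances, and an optional retention program. All of that stands and keeps the point minor.

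Several stronger readings are tempting, and the documents do not support them:

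- **More than half the cohort drops out of the test.** This follows only if a 2-year allowance repeats every 2 years for a decade.
- **The intermediate scores are discarded.** They are summarised by visit and are only left out of the test. KSS is not collected yearly.
- **The test overstates improvement.** Removing baseplate revisions makes this plausible, but most missing cases may be deaths or losses, and nothing shows how they fared.
- **All implant failures are excluded.** Only baseplate revision ends participation; revisions of other components stay in.

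The wording on time could also mean a paired test at each visit through year 10. Each such test would use every case seen at that visit, which eases the problem at early visits. Each would still be a complete-case analysis, so the weakness at 10 years remains.

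A mixed model does not by itself settle the matter either. It assumes data are missing at random, and for revised or deceased patients it projects scores as if the event had not happened. That objection is right, and the fix has to deal with it.

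**Conclusion.** The point holds as a low-cost improvement. The only test named for long-term change is a completer analysis of cases that are alive, in follow-up and still have the tibial baseplate. Scores already collected from the other cases do not enter it.

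Between about 53 and 198 of 356 cases (15% to 56%) would be left out, depending on how the 15% is read over 10 years. The resulting shift in mean OKS change is about 0.5 to 2.8 points upward under an assumed 3 to 5 point gap, and zero with no gap. It is downward if those who left had improved more. Neither the retention range nor the gap comes from the documents. The gain in precision from the earlier scores is expected but has not been quantified here. The primary endpoint and the 2-year secondary comparison are unaffected.

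**What to change.** In section 9.4.1:

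1. Make the main analysis of change in Cohort 1 a mixed model for repeated measures on all scheduled scores of each instrument. Include preoperative score and visit as terms, with repeated measures within patient. Report the model-based change at 2, 5 and 10 years.
2. State that scores are modelled while the patient is alive with the baseplate in place, and report deaths and baseplate revisions alongside.
3. Add a sensitivity analysis that assumes worse scores in dropouts, for example a delta adjustment over a stated range.
4. Keep the paired t-test, labelled as completers only with its number of cases, and say whether it is run at 10 years only or at each visit.

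The cost is revised wording in the statistical plan and modest extra programming in SAS, which the plan already uses. No new data are needed. The downside is that the model relies on data being missing at random, which is why step 3 belongs with it.

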#### **9.4.2 Sample Size Justification**

With a reference value of 99% for the success rate at 2 years, under the assumptions of 5% significance level (or 95% one-sided confidence interval), 95% power, 2% non-inferiority margin, the sample size is 267. After factoring a 15% lost to follow-up rate, the final sample size is 315 for the primary endpoint. An enrollment objective of 356 cases in Cohort 1 (cementless) was selected to power the primary objective of this study. In addition, 144 cases will be enrolled in Cohort 2 (cemented) to serve as a concurrent control for one of the secondary objectives.

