### **9.1.3 Primary Efficacy Analysis**

The primary hypothesis to be tested will be that the success rate at 2 years postoperative with the Triathlon Tritanium Tibial Baseplate for Cohort 1 (cementless) is not worse than 99% with a non-inferiority margin of 2%.

That is, the following hypothesis will be tested:

$H_0: Pt \leq 99\% - 2\%$   $H_A: Pt > 99\% - 2\%$

Here, Pt is the success rate at 2 years postoperative with the Triathlon Tritanium Tibial Baseplate for Cohort 1 (cementless).

A 90% two-sided confidence interval will be computed for the success rate at 2 years. If the lower bound of the confidence interval is greater than 97%, then the non-inferiority hypothesis will be supported.

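### The primary confidence-interval rule has about 72% power at n = 267 for a true 99% success rate, not 95%, and the unnamed interval method can decide pass or fail

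*Combined protocol and SAP*

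**What the plan says.** Section 9.1.3 sets the null hypothesis at a 2-year success rate of 97% or lower (99% less a 2% margin). The analysis is: "A 90% two-sided confidence interval will be computed for the success rate at 2 years". The decision rule is: "If the lower bound of the confidence interval is greater than 97%, then the non-inferiority hypothesis will be supported". No interval method is named.

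Section 9.4.2 begins "With a reference value of 99% for the success rate at 2 years", takes a 5% significance level and continues "or 95% one-sided confidence interval), 95% power, 2% non-inferiority margin, the sample size is 267". It then says "After factoring a 15% lost to follow-up rate, the final sample size is 315 for the primary endpoint" and "An enrollment objective of 356 cases in Cohort 1 (cementless) was selected to power the primary objective of this study". It names no formula and gives no expected true rate apart from the 99% reference.

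Section 9.4.4 bases the primary analysis on a per-protocol population of "all non-censored subjects who receive the study devices and are available for efficacy evaluation".

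**The concern.** A trial of 267 cases at 99% success expects 267 × 0.01 = 2.67 failures. A normal approximation is unsafe with so few events, and here it uses the smaller of two very different variances. At the 97% boundary the variance is 0.97 × 0.03 = 0.0291; at 99% it is 0.99 × 0.01 = 0.0099. The ratio is 2.94.

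Two things are at stake. A device that truly meets the 99% reference could miss its primary endpoint far more often than the 5% implied by 95% power. And common interval methods allow different numbers of failures at the same n, so leaving the method open leaves the primary conclusion open until the data are seen.

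**Working it through.** **Inputs.** Reference rate 99%, one-sided 5% level, 95% power, 2% margin, 15% loss and 356 enrolled come from 9.4.2. The 97% null and the 90% two-sided interval rule come from 9.1.3. The endpoint is treated as a simple proportion, following 9.4.4. The true rate is taken as 99%, the value that reproduces 267.

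**Step 1: reproduce 267 and 315.** With z = 1.645 for both alpha and power, and the variance at 99%:

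n = (1.645 + 1.645)² × 0.99 × 0.01 / 0.02² = 267.85

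This is 267 after truncation. Then 267 / 0.85 = 314.1, rounded up to 315. Other formulas do not give 267: the score formula gives 494, the null variance alone 788, and a two-sided 5% Wald calculation 322. So 267 is not an arithmetic slip; the approximation is the problem.

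**Step 2: evaluate the 9.1.3 rule exactly.** For each n, let c be the largest number of failures for which the lower limit of the 90% two-sided interval exceeds 97%. Then:

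- power = P(X ≤ c) with X ~ Binomial(n, 0.01)
- type I error = P(X ≤ c) with X ~ Binomial(n, 0.03)

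The 15% loss applied to 356 gives 356 × 0.85 = 302.6 evaluable, so both 302 and 303 are shown. Cells give c / power / type I error.

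| Evaluable n | Clopper-Pearson | Wilson | Wald |
|---|---|---|---|
| 267 | 3 / 72.1% / 4.0% | 3 / 72.1% / 4.0% | 4 / 86.8% / 9.6% |
| 302 | 3 / 64.3% / 1.9% | 4 / 81.3% / 5.05% | 5 / 91.5% / 10.9% |
| 303 | 4 / 81.1% / 4.96% | 4 / 81.1% / 4.96% | 5 / 91.4% / 10.7% |
| 315 | 4 / 79.0% / 3.9% | 4 / 79.0% / 3.9% | 5 / 90.1% / 8.8% |
| 356 | 5 / 85.1% / 4.3% | 5 / 85.1% / 4.3% | 6 / 93.1% / 8.9% |

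**Step 3: search every n from 267 to 356.** The highest power is 86.1% for Clopper-Pearson (n = 348), 87.3% for Wilson (n = 339) and 94.7% for Wald (n = 334, type I error 12.5%). None reaches 95%. Wald type I error is never below 6.5% (n = 333). Wilson exceeds 5% at some n, up to 5.9% (n = 294). Clopper-Pearson never exceeds 5%.

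**Step 4: can the method decide the result?** Lower limits for three possible outcomes:

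| Failures / n | Clopper-Pearson | Wilson | Wald |
|---|---|---|---|
| 4 / 267 | 96.61% fail | 96.71% fail | 97.28% pass |
| 4 / 302 | 96.99% fail | 97.08% pass | 97.59% pass |
| 5 / 303 | 96.56% fail | 96.65% fail | 97.15% pass |

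Exactly five failures in 303 has probability 10.3% at a true 99% and 5.7% at a true 97%.

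**The case against.** **The true rate may exceed 99%.** Section 9.4.2 calls 99% a reference value, not the rate expected of the device. At a true 99.5%, Clopper-Pearson power would be 95.4% at 267 and 98.1% at 303. This stands as a condition on the power figures. But the plan states no rate above 99%, its own 267 implies 99%, and a higher rate would not settle the interval method.

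**A Kaplan-Meier estimate might be intended.** Section 9.4.1 plans a Kaplan-Meier curve for baseplate revision or removal for aseptic loosening, and 9.1.3 does not explicitly exclude that estimator. However, 9.4.1 only displays the curve, 9.1.3 does not link its interval to it, and 9.4.4 limits the analysis to non-censored subjects. A simple proportion is the natural reading. If Kaplan-Meier is meant, the plan still needs to say so and name its interval.

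**More cases may be evaluable than 15% loss suggests.** Section 7.5.1 provides that when an in-person visit is not possible, "a Follow-up Questionnaire will be completed via mail, online completion (if available), or subject telephone interview". That may help, but with all 356 evaluable, Clopper-Pearson power is still 85.1%.

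**Clopper-Pearson is partly a preference.** If each of the 356 cases is lost independently with probability 15% (an assumption), Wilson averages about 80% power and 4.7% type I error, against about 73% and 3.4% for Clopper-Pearson. That trade-off is real. Wilson does not hold 5% at every n; the sponsor could choose it knowingly, but should choose in advance.

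**Low power mainly risks a false failure.** This is correct for Clopper-Pearson. The inflated risk of a false claim arises with Wald, which the plan neither selects nor rules out.

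**Conclusion.** The concern holds. The 95% power and 5% level in 9.4.2 cannot both be true of the 9.1.3 rule at a true 99% success rate. At 267 evaluable, power is 72.1% with Clopper-Pearson or Wilson. Wald gives 86.8%, at nearly twice the stated type I error. Enrolling 356 does not restore the claim.

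At the plan's own 15% loss, the chance that a 99% device fails under Clopper-Pearson is 18.9% at 303 evaluable and 35.7% at 302, not 5%. Under Wald at 303, a device at the unacceptable 97% passes 10.7% of the time.

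These figures assume a true rate of 99%, a simple proportion and independent cases. The last is not assured: enrolment is counted in cases, and the radiographic appendix and the Knee Society forms foresee bilateral subjects.

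This must be fixed, because the interval choice can reverse the primary conclusion and can be prespecified only before the data are analysed.

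**What to change.** **Section 9.1.3.** Name an interval that holds the 5% level. For example:

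> Non-inferiority is concluded if the one-sided 95% Clopper-Pearson lower bound for the 2-year success rate, calculated as a simple proportion, is greater than 97%. The maximum number of failures allowed is 3 for 257–302 evaluable cases, 4 for 303–347 and 5 for 348–356. Below 257 evaluable cases the lower-bound rule applies directly.

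**Section 9.4.2.** Keep 356 enrolled. Replace the claim of 95% power at 267 with exact power at a true 99%. Give 64% at 302 evaluable and 81% at 303 equal prominence, because 15% loss falls between them, and add 85% if all 356 are evaluable. State that 99% is the assumed true rate. If the sponsor expects a higher rate, state and justify it, and give the power at that rate as well.

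**Cost.** Rewording of two sections before the 2-year analysis. The stated power becomes less favourable. There are no extra patients and no change to the 97% threshold.
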